3.2 Primary Study Endpoints

The primary study endpoint for the open fracture cohort (cohort 1) is SSI using the CDC National Healthcare Safety Network reporting criteria (<https://www.cdc.gov/nhsn/pdfs/pscmanual/9pscssicurrent.pdf>) within 12 months of fracture.

The primary study endpoint for the cohort of patients with complications, (cohort 2) is treatment failure (either persistent SSI using the CDC National Healthcare Safety Network reporting criteria or persistent nonunion requiring repeat surgical procedure).

The primary study endpoint for the closed fracture cohort (cohort 3) is SSI using the CDC National Healthcare Safety Network reporting criteria.

3.3 Secondary Study Endpoints

The secondary endpoint for all cohorts is unplanned fracture-related reoperation within 12 months of the initial open fracture. This endpoint has been used in previous fracture trials and is defined as any unplanned surgery that occurred from the time of index surgery to 12 months post-fracture that is associated with a wound healing problem, an infection at the operative site or contiguous to it, or fracture delayed union/nonunion.

4 Subject Selection and Withdrawal

4.1 Patient Selection

Consecutive patients 18 years of age or older who present to DHMC with an open fracture will be considered for the open fracture cohort (Cohort 1). Fracture patients who present with a complication (either SSI or nonunion) following fracture fixation or joint fusion will be screened for the complication cohort (Cohort 2). Patients who present to DHMC with a closed fracture will be screened for the closed fracture cohort (Cohort 3).

4.2 Inclusion Criteria

The following criteria must be met by study subjects to be eligible for study enrollment:

Open Fracture Cohort (Cohort 1)

- (1) Patients 18 years of age or older.
- (2) Open extremity fracture.
- (3) Planned definitive fracture management with external fixation, internal fixation, or joint fusion.
- (4) Will have all planned fracture care surgeries performed by a participating surgeon or delegate.
- (5) Provision of informed consent.

Established SSI Fracture Cohort (Cohort 2)

- a. Patients 18 years of age or older.
- b. Extremity fracture.
- c. Prior definitive fracture management with external fixation, internal fixation, or joint fusion.
- d. Superficial, deep, or organ space SSI (as per CDC criteria) at the fracture site that requires operative management.
- e. Will have all fracture care surgeries performed by a participating surgeon or delegate.
- f. Provision of informed consent.

Closed Fracture Cohort (Cohort 3)

- a. Patients 18 years of age or older.
- b. Closed extremity fracture.
- c. Planned definitive fracture management with external fixation, internal fixation, or joint fusion.
- d. Will have all planned fracture care surgeries performed by a participating surgeon or delegate.
- e. Provision of informed consent.

4.3 Exclusion Criteria

The following criteria would exclude a subject from study enrollment:

Open Fracture Cohort (Cohort 1)

- (7) Fracture of the hand.
- (8) Iodine allergy.
- (9) Received previous surgical debridement or management of their fracture at a non-participating hospital or clinic.
- (10) Open fracture managed outside of the participating orthopaedic service.
- (11) Chronic or acute infection at or near the fracture site at the time of initial fracture surgery.
- (12) Burns at the fracture site.
- (13) Incarceration.
- (14) Expected survival of less than 90 days.
- (15) Problems, in the judgment of study personnel, with maintaining follow-up with the patient.

Established SSI Fracture Cohort (Cohort 2)

- a. Fracture of the hand.
- b. Iodine allergy.
- c. Received previous surgical debridement to manage the SSI.
- d. Incarceration.
- e. Problems, in the judgment of study personnel, with maintaining follow-up with the patient.

Subset: DCE-MRI (Cohort 2-1)

- f. the presence of an electronic implant, such as a pacemaker
- g. the presence of a metal implant, such as an aneurysm clip
- h. the presence of other contraindication(s), as determined by the MRI technologists and radiologists.
- i. A history of allergy to iodides

j. A GFR < 30 ml/min as determined by blood test on the day of NIR/MR imaging, or from lab results within 3 months of DCE-MRI for this study

Closed Fracture Cohort (Cohort 3)

- a. Fracture of the hand.
- b. Iodine allergy.
- c. Chronic or acute infection at or near the fracture site at the time of initial fracture surgery.
- d. Burns at the fracture site.
- e. Incarceration.
- f. Expected survival of less than 90 days.
- g. Problems, in the judgment of study personnel, with maintaining follow-up with the patient.

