Risk of dynamic contrast-enhanced magnetic resonance imaging (DCE-MRI): The risks associated with Gd contrast-enhanced MR are minimal. Gd-DTPA is an FDA-approved contrast agent and is widely used with few complications. The contrast injection procedures follow FDA-approved guidelines which are accepted as part of standard care in this setting. Consenting participants will have an intravenous catheter placed in an arm vein prior to their MRI examination by a trained MRI technologist conforming to the standard clinical methods used at DHMC.

Serious reactions to the gadolinium (Gd) are extremely rare and are primarily limited to nausea and vomiting. In response to the FDA notification regarding the potential association of nephrogenic sclerosing fibrosis (NSF) and intravenous gadolinium administration (primarily gadodiamide (Omniscan)), the Department of Radiology has developed a protocol which we will follow:

1. Identify the patients at higher risk of developing NSF (at the time of scheduling or before). Patients at risk include:

- Patients > 50y
- Patients already on dialysis
- Patients with known renal insufficiency but not currently on dialysis
- Diabetic patients

- Patients with known cardiovascular disease
- Patients who will be receiving high dose gadolinium (e.g. MR angiograms)
- Hypertensive patients

2. Obtain estimated Glomerular filtration rate (GFR) on this higher risk group of patients (unless already on dialysis).

- If a GFR value has been checked and is available in the patient's medical record within 1 month of contrast-enhanced MR, that value will be acceptable.
- If the participant is not a patient at DHMC, a "stat" GFR will be performed at DHMC one (1) hour prior to contrast-enhanced MR scan.

Subjects with a GFR <30 ml/min. will be considered ineligible for the contrast enhanced MRI portion of the study.

GFR values will not be sought at the time of scheduling on low risk patients, but the scheduler will check medical records at the time of the scan to see if an incidental GFR value is available.

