A Pulse dye densometer (Pulsion Medical Systems), similar to a pulse oximetry probe, will be placed on the patient's finger to acquire an arterial blood input function during ICG injection. After exposure but prior to debridement, 0.1 mg/kg ICG will be injected intravenously. Video rate ICG fluorescence images will be acquired 20 seconds before and 4 minutes after ICG injection. Debridement will then proceed per standard of care. The wound will be irrigated with a minimum of 3 liters irrigation with normal saline. After irrigation and debridement is completed, 0.1 mg/kg ICG will be injected intravenously again and video rate ICG fluorescence images will be acquired 20 seconds before and 4 minutes after ICG injection. There will be a minimum of 5 minutes between ICG infusions to allow ICG to wash out of tissues.

A subset of 30 eligible consenting patients with post-fracture complications will undergo surgical treatment for their infection in CIS at DHMC. Patients receiving surgery in the CIS will be required to sign an additional CIS-specific consent document. For the patients who didn't receive contrast MRI in 48 hours prior to the

operation, after exposure and removal of hardware but prior to pre-debridement ICG injection, four MRI fiducials will be placed on the four corners of the damaged bone area and the MRI sequences will be acquired. Sequences will include a localizer, coronal T1 fast spin echo (FSE), axial short-tau inversion recovery (STIR), a T1 mapping sequence consisting of a T1-weighted 3D FLASH sequence with at least 3 different flip angles, and DCE acquisition, consisting of 3D FLASH sequences before and after the intravenous administration of 0.2 mL/kg Gadoterate meglumine (Dotarem®). The T1 mapping and DCE sequences will be acquired in the same plane (either the coronal or axial) for all patients. The protocol for the DCE acquisition has already been optimized for current clinical applications in the imaging of both bone and soft tissue tumors. For the patients who received MRI within 48 hours prior to the operation, we may use their pre-operation MRI, instead of intra-operative MRI.

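### For the DCE-MRI subset, Sections 1.5.1 and 4.3 set different limits on how old a GFR result may be (1 month against 3 months), leave unclear who must have one, and Section 6 names a different contrast agent from the risk text

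*Combined protocol and SAP*

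**What the plan says.** Three sections of the protocol bear on screening for the contrast MRI, and two bear on the agent's name only.

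- **Section 1.5.1 (Potential Risks)** says the study will follow a Radiology protocol written in response to the concern about nephrogenic sclerosing fibrosis (NSF). It lists a higher-risk group and instructs staff to "Obtain estimated Glomerular filtration rate (GFR) on this higher risk group of patients (unless already on dialysis"). A value is usable if it is in the patient's "medical record within 1 month of contrast-enhanced MR, that value will be acceptable". For a participant who is not a DHMC patient, a stat "GFR will be performed at DHMC one (1) hour prior to contrast-enhanced MR scan". For the rest, "GFR values will not be sought at the time of scheduling on low risk patients"; the scheduler only checks the record for an incidental value when the scan is done. A GFR below 30 ml/min makes the subject ineligible for the contrast MRI.
- **Section 4.3 (Exclusion Criteria, DCE-MRI subset), criterion j** excludes a GFR below 30 ml/min, determined by a blood test on the imaging day, "or from lab results within 3 months of DCE-MRI for this study". It mentions no risk group and no dialysis exception.
- **Section 6 (Study Procedures, Surgical Procedures)** specifies "intravenous administration of 0.2 mL/kg Gadoterate meglumine" for the DCE acquisition.
- **Section 1.4 (Dose Rationale)** and Section 1.5.1 name Gd-DTPA instead. Section 1.5.1 says "Gd-DTPA is an FDA-approved contrast agent and is widely used with few complications". The List of Abbreviations spells Gd-DTPA out as one specific compound.

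**The concern.** The GFR cut-off is the protocol's stated safeguard against NSF, in a study that promises participants no direct benefit. The safeguard depends on which result is compared with 30. If two operative sections allow results of different ages, two screeners acting in good faith can reach different decisions on the same patient. A monitor could not call either one a deviation, because each has a section to cite. The exclusion list is also what a screener normally works from, and it carries the longer window.

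The contrast agent is a separate matter of labelling. The sentence that reassures the reader about the agent names a compound other than the one in the procedure.

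**Working it through.** The plan has no figure to reproduce here. The check is a side-by-side reading, followed by patients with assumed values.

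**1. Age of the result.**
- Section 1.5.1: chart value up to 1 month old, in the higher-risk group not on dialysis.
- Section 4.3, criterion j: same-day test, or a result up to 3 months old, with no group specified.
- Ratio of the two windows: 3 / 1 = 3.
- Cut-off: below 30 ml/min in both, for the same contrast MRI. They are therefore not rules for different purposes.
- Precedence: none stated.

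**2. When the difference changes a decision.** Take a higher-risk DHMC patient, not on dialysis, whose latest GFR is two months old. The GFR values below are assumed for illustration.
- *Old value 45, new value 25.* Criterion j can rest on 45, which is not below 30, so the patient is not excluded. Under 1.5.1 the result is past 1 month, a new test is taken, 25 is below 30, and the patient is ineligible.
- *Old value 25, new value 40.* Criterion j can rest on 25 and exclude. Section 1.5.1 uses 40, and the patient is eligible.
- *Old value 45, new value 40.* Both sections lead to the same decision. The only difference is one extra test.

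The decision therefore differs only when the old and new values straddle 30, and it can differ in either direction. If the latest value is within 1 month, both windows are met and there is no conflict on age.

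**3. Who must have a GFR.**
- Section 1.5.1 obtains it in the higher-risk group and does not seek it at scheduling in low-risk patients.
- Criterion j has no risk-group limit, but does not say in words that everyone is tested.
- Illustration: a low-risk patient with no GFR on file and a true value of 25. Under 1.5.1 no value is sought at scheduling and the scan can go ahead. A day-of test under criterion j would exclude the patient. If no test is done, criterion j is neither met nor ruled out.
- This is a gap between the sections, not an express contradiction.

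**4. Contrast agent.** Sections 1.4 and 1.5.1 name Gd-DTPA; Section 6 names gadoterate meglumine. No eligibility rule in Section 4.3 or 1.5.1 refers to which of the two is given, so this mismatch changes no patient's eligibility.

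**The case against.** The strongest case on the other side has four parts.

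- *The two windows can be met together.* A value within 1 month satisfies both, and Section 1.5.1 commits the team to the Radiology protocol whatever Section 4.3 allows. Criterion h also leaves other contraindications to the MRI technologists and radiologists. This stands as a limit on the practical risk. It does not remove the conflict, because nothing tells the screener that 1.5.1 overrides criterion j.
- *An older result is not a failure under 1.5.1.* This stands. A reader might infer that a patient with a two-month-old GFR passes 4.3 and is ineligible under 1.5.1. The text does not support that: the older result leads to a new test, and the new value decides.
- *Not everyone in the subset is affected.* This stands. A reader might infer that every MRI patient is exposed to the look-back conflict. The 1-month rule covers only the higher-risk group not on dialysis, and within it the conflict arises only when the latest value is 1 to 3 months old. Nor can one say that criterion j requires a test in everyone; that would be inference.
- *The agent mismatch is narrow.* This stands too. One might infer that it alters eligibility, or that the whole risk statement was written for another drug. Only the reassurance sentence is specific to Gd-DTPA. The text on serious reactions and NSF speaks of gadolinium in general and singles out gadodiamide. Whether risk differs between the two named agents cannot be judged from the documents.

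**Conclusion.** The look-back contradiction is certain from the text: 1 month in Section 1.5.1, 3 months in criterion j, one cut-off and no precedence. It affects higher-risk patients not on dialysis whose latest GFR is 1 to 3 months old, and it alters eligibility only where the old and new values lie on opposite sides of 30 ml/min. The documents give no count of such patients, so the frequency cannot be stated.

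Who must be tested is an ambiguity and is less certain than the look-back conflict. The agent mismatch is plain, but it is a labelling error with no effect on eligibility.

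The conclusion rests on one reading: that in the higher-risk group Section 1.5.1 calls for a fresh GFR when no chart value within 1 month exists. The section says this by implication, since it tells staff to obtain a GFR and lists the within-1-month value as the acceptable substitute.

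The point is confined to Cohort 2-1. It does not touch the primary endpoints, the power calculations or the main analyses. It should be corrected because it concerns a stated safeguard and costs almost nothing to repair.

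**What to change.** Reconcile Sections 1.4, 1.5.1, 4.3 and 6 so that the protocol contains:

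1. one look-back period for GFR, stated identically in Sections 1.5.1 and 4.3;
2. one statement of who must have a GFR before contrast, covering low-risk patients, patients on dialysis (whom 1.5.1 exempts from testing without saying whether they may have the contrast MRI) and participants who are not DHMC patients;
3. one named contrast agent throughout, with risk text that matches it.

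Which window, which testing rule and which agent apply is for the sponsor and radiology to decide; this review takes no position. The cost is an edit to protocol wording, and to the consent text if it repeats the affected statements. No change to sample size or analysis follows.

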4.4 Subject Recruitment and Retention

Participation in this research requires informed consent according to Institutional Review Board (IRB) guidelines and a signed IRB-approved Consent Form as the means of documenting this understanding. Patients receiving surgery in the CIS will be required to sign an additional CIS-specific surgical consent document.

Potential recruits are instructed that their participation is completely voluntary and that their medical care will not be altered in any way should they elect not to participate at any time prior to surgery. Subjects are recruited from patients presenting or referred to Orthopedic Department at Dartmouth-Hitchcock Medical Center for treatment and meeting protocol inclusion criteria. This study requests a partial waiver of HIPAA for recruitment purposes. The partial waiver would allow for the surgeon to share with the research coordinator the patient name, sex, MRN number, age, underlying conditions as well as type and location of injury. There is an adequate plan to protect identifiers from improper use and disclosure as information will only be used by study team members to determine whether a patient may be eligible. Information will only be communicated and stored using D-HH approved secure platforms. Information is only being used to determine if a patient is eligible for the study, for recruitment purposes. Once approached, if a patient is not interested, information will be destroyed. Protected health information will not be re-used or disclosed for another purpose. It will only be used for recruitment. This research could not practically be done without a partial waiver of HIPAA. This information is needed for recruitment. Patients will sign a full HIPAA Authorization when consenting to the study.

Potential subjects may be contacted by [name], [name] or another surgeon in the Orthopaedic department to learn about the study and participation. Subjects will be invited to participate in this study by a member of the Orthopaedic Department, which will occur either at the time of consultation with the surgeon about the candidate's standard-of-care procedures or at another time agreed to by the potential participant, the candidate's surgeon and/or [name] and/or [name] or their designee. No advertisements or other promotional material will be used. No finder fees or recruitment incentives will be offered. Women of child bearing potential are eligible for enrollment into this study because ICG administration is not considered to present any additional risk for these women. The study will exclude women who are pregnant or breast-feeding as indicated in the exclusion criteria. Women of child-bearing potential, if asked to participate, will be given a pregnancy test as part of their standard of care pre-operative testing to confirm pregnancy status before administration of ICG.

Subjects enrolled into this study prior to 01Nov2020 will be re-consented in order to allow for the use of their data in the following applicable studies:

Fluorescence Based Measurement of Bone Perfusion in Infection (STUDY 02000374)
ICG Fluorescence Imaging in Open Trauma (STUDY 02000365)

All follow-up visits are within standard practice for these injuries/diagnoses.

Several additional strategies may be used to maximize follow-up including: 1) at the time of enrollment each participant will provide their own telephone number, as well as the name and address of a primary care physician, and the names and phone numbers of three people at different addresses with whom the participant does not live and who are likely to be aware of the patient's whereabouts; 2) participants will receive a reminder card upon discharge for their next follow-up visit by the clinical site study personnel; 3)

participants will receive text message reminders; 4) follow-up will coincide with normal surgical fracture clinic visits; and 5) if a participant refuses or is unable to return for the follow-up assessment, study personnel will determine his/her status with regards to major study outcomes by telephone, text, mail or email contact with the participant or the provided alternate contacts.

4.5 Early Withdrawal of Subjects

4.5.1 When and How to Withdraw Subjects

Participants will be removed from the protocol if: Study imaging is not completed for any reason.

1) The subject withdraws consent.

The subject has an occurrence of a significant clinical event that precludes imaging.

2) The subject becomes pregnant.

If a participant is withdrawn from the protocol, the PI will mark the data of this subject as "withdrawn" and will add a detailed explanation about the cause of withdrawal in the database.

4.5.2 Data Collection and Follow-up for Withdrawn Subjects

For subjects who withdraw after the intraoperative imaging, we will follow-up to see if they still complete their clinical follow up in six months. For subjects who eventually finish their all clinical follow up visits, we will acquire their follow up results to include these subjects in the statistical analysis portion that only involves the intraoperative image data and infection status.

5 Study Drug and device

[figure not shown]

Figure (a): Schematic sketch of ICG fluorescence imaging.

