The need for repeat debridement or tissue cultures will be left up to the treating surgeon. If repeat debridement is needed, pre- and post-debridement quantitative ICG fluorescence images will be obtained at each procedure. If the skin wound is unable to be closed, it will be left open with a sterile dressing until delayed coverage in collaboration with plastic surgery.

Upon admission and throughout the hospital course, patients will be treated with antibiotics per standard of care by the orthopaedic service or in collaboration with infectious disease recommendations. Management of study patients including clinical and radiographic assessments will not differ from standard of care.

Study participants will be followed at 6 weeks, 3 months, 6 months, 9 months and 12 months from their fracture (open and closed fracture cohorts) and from the date of consent (complication cohort), respectively. Final follow-up will be at 6 months to capture all infectious complications (Figure c.2)³⁵. If a participant does not return to clinic, follow-up may be conducted by telephone. SSI and unplanned fracture-related reoperations will be identified at the time of diagnosis/occurrence and/or during each participant clinical assessment and medical record review that will occur during their routine outpatient clinic visits.

7 Statistical Plan

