7.3 Subject Population(s) for Analysis

This study will involve consecutive patients 18 years of age or older who present to DHMC with an open fracture will be considered for the open fracture cohort (Cohort 1). Similarly fracture patients who present with an SSI following fracture fixation or joint fusion will be screened for the fracture SSI cohort (Cohort 2). Patients who present to DHMC with a closed fracture will be considered for the closed fracture cohort (Cohort 3). The image and clinical outcome data of all patients involved in this study will be analyzed.

8 Safety and Adverse Events

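### Section 4.5.2 admits post-imaging withdrawals to the analysis on condition that they finish all visits, gives no rule for an SSI recorded before withdrawal, and conflicts with section 7.3

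*Combined protocol and SAP*

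**What the plan says.** Section 4.5.2 of the combined protocol and SAP covers subjects who withdraw after the intraoperative imaging. It first says that "we will follow-up to see if they still complete their clinical follow up in six months". It then says: "For subjects who eventually finish their all clinical follow up visits, we will acquire their follow up results to include these subjects" and limits their use to a part of the analysis, "in the statistical analysis portion that only involves the intraoperative image data and infection status". Nothing is said about withdrawn subjects who do not finish, or about outcomes recorded before the withdrawal.

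Four other places bear on the point:

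- Section 4.5.1 has the data of a withdrawn subject marked as such, and the investigator "will add a detailed explanation about the cause of withdrawal in the database". No deletion is stated. Withdrawal of consent is one of the listed reasons for removal.
- Section 7.3 defines the analysis population: "The image and clinical outcome data of all patients involved in this study will be analyzed".
- Section 6 (Study Procedures, under Surgical Procedures) says that "SSI and unplanned fracture-related reoperations will be identified at the time of diagnosis/occurrence and/or during each participant clinical assessment". It also says: "If a participant does not return to clinic, follow-up may be conducted by telephone".
- Section 4.4 says that for participants who refuse or cannot attend, "study personnel will determine his/her status with regards to major study outcomes by telephone, text, mail or email contact".

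Section 3.2 sets the cohort 1 primary endpoint as SSI within 12 months of fracture.

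**The concern.** Take a patient who is imaged at surgery, is diagnosed with an SSI at six weeks, then withdraws and misses the last visit. Predictor and outcome are both known. Under section 4.5.2 the only stated way into the analysis is to finish all visits, so an analyst who follows it literally leaves this patient out. An analyst who follows section 7.3 keeps the patient in. The plan does not say which section prevails, so the analysed set could be settled after outcomes have been seen.

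This matters because SSIs are the scarce group. Cohort 1 expects 16 against 144 without SSI, and the precision of the perfusion comparison comes almost entirely from the 16. Selection on completing follow-up can also distort the estimated SSI rate. It can distort the comparison of perfusion if, within an outcome group, completion is related to perfusion.

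**Working it through.** **1. The passages side by side.** If 7.3 governs, the completion condition in 4.5.2 has no purpose. If 4.5.2 governs, 7.3 is not true as written. Section 6 identifies SSIs when they occur as well as at visits, so finishing every visit is not needed to know that an SSI has happened.

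**2. The plan's own power figure.** Inputs from section 7.1, cohort 1: 16 SSI and 144 non-SSI, mean difference 24 a.u., SDs 30 and 15, type I error 5%. Section 7.1 does not state sidedness; two-sided is assumed here. For a Welch t-test with noncentral t:

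- SE = √(30²/16 + 15²/144) = √(56.25 + 1.5625) = 7.60
- noncentrality = 24/7.60 = 3.16, Satterthwaite df = 15.8
- power = 84.1%, against 86% stated.

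The same method for cohort 2 (22 against 52) gives 92.9%, against 93% stated. The method therefore reproduces the plan to within two points. Note that 56.25 of the 57.81 in the variance comes from the SSI group.

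**3. What the drop-out allowance already covers.** Section 7.1 enrols 160 × 1.10 = 176, so 176 − 160 = 16 drop-outs are planned. At 10%, 176 patients give 17.6 SSIs. Losing 16 patients at the same 10% rate removes 1.6 and leaves 16. Only losses beyond that reduce the 16.

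**4. Illustration of further losses.** Non-SSI is held at 144. The last column is the SSI rate that the 16 drop-outs would need, (17.6 − SSIs analysed)/16.

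| SSIs analysed | SE | Noncentrality | df | Power | SSI share of analysed | SSI rate needed among drop-outs |
|---|---|---|---|---|---|---|
| 16 | 7.60 | 3.16 | 15.8 | 84.1% | 10.0% | 10% |
| 15 | 7.85 | 3.06 | 14.7 | 81.5% | 9.4% | 16% |
| 14 | 8.11 | 2.96 | 13.6 | 78.4% | 8.9% | 22.5% |
| 12 | 8.75 | 2.74 | 11.5 | 70.8% | 7.7% | 35% |

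In cohort 2, losing 2 or 4 of the 22 failures takes 92.9% to 90.5% or 87.2%. The documents give neither the number of post-imaging withdrawals nor their SSI rate, so none of these rows is a forecast.

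**5. Length of follow-up.** The check in 4.5.2 is at six months; the cohort 1 endpoint runs to 12 months. A withdrawn subject who satisfies 4.5.2 may still have SSI status for only half the endpoint window.

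**The case against.** A reader might infer that the plan orders recorded SSIs to be dropped. It does not. The word only in 4.5.2 limits the part of the analysis, not the subjects, and the sentence can be read as a permission to collect results after withdrawal. Section 4.5.1 flags withdrawn data without deleting them, an SSI at six weeks would already be on record under section 6, and 7.3 would keep it. This stands: the exclusion is implied by the only stated route into the analysis, not stated. What remains is a gap and a conflict between two sections.

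A reader might also infer that every patient with incomplete follow-up is affected. That goes too far. Section 4.5.2 concerns withdrawn subjects, and sections 4.4 and 6 provide for remote retrieval of outcomes from those who merely miss visits.

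A third tempting reading is that power falls to 78% or 71%. The 16 SSIs are already net of the 10% drop-out allowance. To fall to 14 or 12, the 16 drop-outs would need SSI rates of 22.5% or 35%, and for this rule to be the cause they would have to be post-imaging withdrawals with an SSI already recorded. Nothing in the documents supports that.

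Finally, no direction of bias can be claimed. Complications may bring patients back to clinic, in which case SSIs are retained. Selection that depends on SSI status alone changes the SSI rate but does not bias the difference in mean maximum intensity between the SSI groups.

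**Conclusion.** The point holds as a gap and an internal conflict that should be resolved before analysis. Section 4.5.2, followed literally, leaves out withdrawn patients whose image data and SSI outcome are both known; 7.3 says the opposite. The selection is avoidable, and it falls on a cohort where about 16 events carry the comparison.

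The size cannot be derived from the documents. The power figures (84.1%, 81.5% and 78.4% with 16, 15 and 14 SSIs) assume a two-sided Welch test, the plan's difference and SDs, and losses of SSIs beyond the drop-out allowance. They show sensitivity per lost event, no more. The direction of any bias is unknown. Whether data may be kept after consent is withdrawn depends on consent terms that are not in the reviewed text.

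**What to change.** Replace the completion condition in section 4.5.2 and align it with 7.3:

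- Any imaged subject with an SSI recorded before withdrawal (in cohort 2, treatment failure) is kept in the analysis as an event, where consent allows. Outcomes that arise after withdrawal are used on the same condition.
- A withdrawn subject who is event-free with incomplete follow-up has an unknown outcome and is not counted as non-SSI. Section 7.2 analyses SSI as binary, so entering such subjects with their status at last contact would misclassify some of them. Censor them in a time-to-event analysis, or treat the outcome as missing with a stated method. Simply dropping them while keeping the recorded events would push the SSI rate upward.
- Add one sensitivity table for incomplete follow-up. It should show the number of withdrawn subjects by cohort, their post-debridement maximum intensity, and the primary comparison with the unknown outcomes set all to non-SSI and then all to SSI.
- Reconcile the six-month check in 4.5.2 with the 12-month SSI window in section 3.2.

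The cost is a short text change in 4.5.2 and 7.3, a line in 7.2 naming the missing-outcome method, and one table. Apart from any extension of the six-month check, no new data collection is needed, because SSIs are already recorded when they occur.
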